Participants endorsing suicidality via PHQ-9 #9 > 1 during the screening process will complete a self-report version of the Columbia Suicide Severity Rating Scale (CSSRS). Any positive endorsement of items 3-5 on the CSSRS at the time of enrollment, indicating intent or plan, will immediately trigger notification of study clinicians to initiate outreach procedures to the participant and to community provider or emergency contact. Suicidality expressed during the course of clinical and qualitative interviews, either through discussion, endorsement of suicidality on the MINI mood module, endorsement of items 3, 4, or 5 on the suicidality module of the MINI, or via scoring >2 on the MADRS item 10, will prompt study staff to complete the CS-S with the participant. A positive score on items 3, 4, or 5 of the CS-S administered by staff will also prompt a safety call by study physicians. In addition, subjects will be told by study staff to call their community providers and go to their nearest emergency room. During this risk assessment, study doctors will assess risk and recent symptoms by completing the full version of the CSSRS, collecting information about ideation, intensity of ideation, and suicidal behaviors. Outcome of this assessment will be shared with community providers.

At the time of subject enrollment for the UPWARD Supplemental Arms, participants will be notified of the outreach to their community providers during the informed consent process. Following enrollment, community providers will be sent a letter notifying them of their patient's enrollment in the study and endorsement of suicidal ideation. Aside from the information that is shared during safety outreach to community providers in the parent UPWARD study (patient name, specifics of expressing suicidal ideation - i.e. questions endorsed through self-report questionnaire, date of endorsement), no additional data collected from participants will be shared at the time of initial outreach to community providers or during the qualitative interviews with providers described in Supplemental Aim 1b. During physician safety calls, any information necessary to ensure participant safety (as determined by the study psychiatrist making the phone call) will be shared with their community provider.

Endorsement of items 3-5 on the CS-S prompting a physician safety call has been the threshold used in previous studies at the collaborating site (University of Colorado Boulder). As this is a community-based study with collaboration from community physicians, these providers dictate treatment. As noted above, consent to communicate with these individuals is obtained as a required part of enrollment in the parent grant and will be applied in the supplement. The feasibility of establishing close communication with community-based providers of pregnant women with depression with and without suicidality enrolled in prospective studies is well established from previous federally funded grants conducted by the MGH group over the last 15 years as well as with the randomized participants already enrolled in the parent UPWARD grant. We have also engaged a national leader in the investigation of suicide, [name] (an expert in suicide research and a co-creator of the CSSRS) as a consultant to advise us on the other ways in which the clinical assessment of suicidality may be refined particularly with respect to evaluation of pregnant and postpartum women.

In another potential scenario not directly related to assessment of suicidality but relevant to prospective follow-up, queries may arise from participants' community prescriber or provider regarding changes or reintroduction of pharmacologic treatment during pregnancy or the postpartum period. In this situation, study physicians with expertise in perinatal psychiatry will be available to provide consultation to these providers. This procedure of support to community prescribers has been successfully used by the MGH team across multiple studies in which participants were prospectively followed with standardized instruments during pregnancy and the postpartum period while concurrently followed clinically by community-based prescribers.

There are risks to confidentiality and privacy associated with participation in all research studies and in studies of digital interventions. A number of steps have been taken to safeguard privacy and confidentiality across the study. All study staff will be required to sign statements indicating that they understand confidentiality and agree to protect against risk of confidentiality. Study personnel and materials will assure that participants understand the confidentiality measures taken in this study to protect them and their information. Participants will be invited at any time to share their concerns with the study staff, investigators, or IRB representatives.

Also, participating in this study will involve access to four websites: the MMB website – where the 8-session program will be presented, Qualtrics – where the SRET data and GNAT will be collected, the REDCap website – where the online surveys will be completed, and Calendly to facilitate scheduling. The digital platform for MMB will be hosted at Brella for the study's duration. Direct access to the server is secured by a firewall with IP whitelisting and account verification. HTTPS, SSL access, and user passwords are secured with 256-bit level encryption. Passwords and their associated web access will be deleted from the study registry by study staff at the close of this study or at the participant's termination or completion of the study, whichever is earlier. The study team will have administrative access to the website. Brella is experienced in managing confidential data using encryption and passwords. Calendly uses a secure server and data center accredited under: ISO 27001, SOC 1 and SOC 2/SSAE 16/ISAE 3402 (Previously SAS 70 Type II), PCI Level 1, FISMA Moderate and Sarbanes-Oxley (SOX). Scheduling information that passes through Calendly is encrypted, both in transit and at rest. All connections from the browser to the Calendly platform are encrypted in transit using TLS SHA-256 with RSA Encryption.

Study data will be collected and managed using REDCap. REDCap is a secure web application designed to support data capture for research studies. The database is hosted at the University of Colorado Denver Development and Informatics Service Center (DISC), which will be used as a central location for data processing and management. This project uses REDCap Twilio integrated functionality to allow participants to respond via SMS text message to the questions asked in the positive mood diary. A REDCap and Twilio account are linked together. When a user indicates that an SMS (text) or a call should be sent to a cell phone, REDCap requests that action through Twilio. When a user responds, Twilio relays that information back to REDCap. The data is stored in the REDCap database. Twilio does not store any data nor does it keep a log of its actions. All voice calls and SMS messages will be routed through Twilio's servers, but REDCap goes to great length to ensure that voice call records and SMS transcriptions do not stay in Twilio's logs but are removed shortly after being completed. This is done for security and privacy concerns (e.g., HIPAA), in which participants' phone numbers and their survey responses do not get permanently logged on Twilio's servers but instead remain securely in REDCap.

Another risk to confidentiality involves unauthorized access to a participant's login information if that information is inadvertently left in plain view. Although this risk is not completely preventable, we will instruct participants in the importance of keeping their login information secure and confidential.

The digital MMB program makes available an online community; however, this will be moderated by the research team in order to maximize anonymity. Though unlikely in the context of national recruitment, it is possible that individuals may identify one another despite such efforts and not protect the privacy of other members. We will inform participants of this potential in the consent form, and we will also explicitly ask participants in the process of seeking consent to maintain the privacy of all participants.

We anticipate that the additional 12-months postpartum timepoint (UPWARD-Baby) will not present any additional risk for participants compared to that of the parent study. Because we are asking the PHQ-8 at this timepoint instead of the PHQ-9 (which is what is asked throughout the parent study), we will not learn about suicidal ideation and therefore a safety plan for SI is not needed.

VIII. POTENTIAL BENEFITS

Participants may benefit from ongoing clinical monitoring of depressive symptoms and, in all arms except UPWARD Extension, provision of feedback. In addition, participants assigned to the MMB condition may experience an increase in knowledge about depression and how to decrease future risk for relapse. All participants enrolled in the study will have any benefits afforded by the assessment protocol with respect to the possible early identification of depressive symptom exacerbation and information about accessing national mental health services and potential consultation to their community prescriber. Since contact with the study team will occur at multiple time points, subjects will have the opportunity to easily access experts in the area of depression and pregnancy.

Lastly, subjects will be compensated for their participation. Participants in the parent UPWARD Study will be compensated \$175 for their participation in the study. Participants in UPWARD Extension will be compensated a total of \$140 for their participation in the study. Participants in UPWARD Supplement Arms 1a and 2 will be compensated \$200 for their participation in the study (\$25 more than parent UPWARD study to compensate for participation in qualitative interviews and additional self-report questionnaires). Providers that participate in UPWARD Supplement Arm 1b will be compensated \$75 for their participation in the qualitative interview.

Study physicians with expertise in perinatal psychiatry will be available as a resource to community providers for advice and management of participants' clinical care. If questions arise regarding changes or reintroduction of pharmacologic treatment during pregnancy or the postpartum period, study physicians can provide consultations to these providers, thus spreading clinical knowledge and equipping providers with the tools to provide evidence-driven care.

Recent reviews have called for additional research examining mindfulness-based interventions among adults with suicidal ideation and behavior.²⁶ These recommendations are based, in part, on studies of mindfulness-based cognitive therapy (MBCT) among adults with histories of suicidal ideation and behavior.^{16,27-29} Clinical trials in progress are examining the extension of MBCT for specific populations with suicidal ideation, such as veterans³⁰ and young adults.³¹

Additionally, some evidence suggests specific processes by which these benefits may be conferred in MBCT, such as meta-awareness, specificity of autobiographical memory,^{15,16} the strengths of association between depression symptoms and suicidal thoughts,³² and asymmetry in resting EEG activation.³³ Given this evidence, MMB for Moms may be a promising intervention for pregnant women with suicidal ideation, as it delivers digitally both the content and structure of in-person MBCT. That said, there is also good justification for taking an incremental approach to the use of MMB for Moms with this population.

IX. MONITORING AND QUALITY ASSURANCE

[name] and [name] will co-monitor ongoing safety of study participants. They will provide training to study staff at each site to ensure that all study staff are prepared to implement safety protocols and to identify and review immediately with the study investigators any risk to the safety, privacy, or confidentiality of participants, any problems with data collection or management, or deviations from the protocol. Furthermore, they will be trained in specific protocols in place for study to staff to report any adverse events to the study investigators. Research coordinators will meet twice weekly with the study PIs to review any safety concerns, and there will be weekly project management calls with the PIs and study research coordinators at both sites. Study binders and databases will be reviewed on a continuing basis to monitor accuracy and completion.

A Data Safety Monitoring Board (DSMB) will be established for trial monitoring. The DSMB will consist of four persons, including a psychiatrist with expertise in depression care management, a psychologist with expertise in the design and implementation of pragmatic clinical trials, a Ph.D.-level statistician, and an expert in online intervention or education delivery. None of these persons will be involved directly in the study. The DSMB has agreed to oversee the UPWARD Study and UPWARD-S components. The DSMB will have the following aims:

- To assure the safety, privacy, and confidentiality of human subjects
- To assure the reliability, validity, completeness, and integrity of the data collection, entry, and management process
- To review implementation of the human subjects protocol, including all proposed protocol amendments and modifications
- To review all serious adverse events, less serious adverse events, rates of dropout or study withdrawal, and rates of missing data

The DSMB will have a minimum of two teleconferences per year for the study duration. Members will also meet via email as needed and by teleconference call if serious adverse events attributable to study procedures are reported. Prior to its regular meetings, the study team will prepare reports to the DSMB about progress toward achieving the scientific aims, including study enrollment and patient flow, dropout and retention, data quality, confidentiality, and safety issues. The DSMB also will be provided with blinded reports of intervention effectiveness to inform judgments about the value of interim analyses. Both [name] and [name] will attend all meetings with the DSMB.

The DSMB will issue independent reports to the IRBs and the NIMH summarizing its review of these domains. If the DSMB believes that participants are being endangered, the Board will make recommendations to the NIMH and IRBs as to whether the trial should be stopped or procedures modified. If indicated, the independent reports from the DSMB will suggest ways to reduce risk and improve the quality of care of participants, and ways to improve the reliability, validity, integrity, and confidentiality of the data collection procedures.

An advisory stakeholder panel, composed of prior collaborators and women with perinatal mood and anxiety disorders, will be established to provide advice on study procedures and discuss participation burdens and ease of use. This group will function solely in an advisory capacity, and will not view protected health information, data, or research subject-specific information. We will use this panel to review procedures and various protocols prior to enrollment of subjects to ensure they are reasonable for subject participation.

All participants, regardless of treatment condition to which they have been randomized, will receive one telephone contact per trimester by MGH study staff, who will administer the mood module of the Mini International Neuropsychiatric Interview (MINI)⁴⁰ and who will be blind to randomized condition. Phone interviews will be audio recorded for supervision and data quality insurance purposes. These recordings will help the research team understand how the intervention works and maintain consistency across interviewers. Like all research information, these recordings will be stored on a secure server and kept confidential. All audio files will be labeled with an assigned study code number and will be used for research and teaching purposes only. Audio files will be stored on secure, password protected servers, accessible only to key study personnel.

Research staff will receive intensive training prior to conducting assessments with study participants. Training will include orientation to the MINI, observation of live training interviews, and co-rating of training interviews. Interviewers will need to establish interrater reliability (weighted kappa statistic) $> .80$ before interviewing study participants. Formal supervision of the interviewers and the reliability process will be provided by [name] at MGH.

During the course of the protocol, study and non-study related events such as hospitalization or recurrence of depression may occur; our risk management protocols are in place to address these events as they occur. All study staff are trained and available to manage adverse events. Physicians are available by phone and pager to be informed of serious adverse events. Study investigators will report adverse events to the IRB following the PHRC guidelines, including reporting within 5 business days. Investigators will also report the event to the DSMB, including the details of the event, the severity of any reactions, the phase of the study, and the procedures for its resolution. In addition, the study investigators will ensure that the NIMH Program Officer is informed of any actions taken by the IRB as a result of such events.

These events will be promptly reported to the MGH IRB, according to the Code of Federal Regulations, and the subject's primary care and mental health providers will be informed with the subject's permission.

X. REFERENCES

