Mini-International Neuropsychiatric Interview (MINI). The MINI is a valid, structured diagnostic tool that assesses Axis I and II disorders in accordance with DSM-IV symptom criteria. The MINI will be used to establish baseline diagnoses for each participant, and to ensure eligibility criteria are met (e.g. rule out diagnoses of bipolar disorder, psychosis, or substance abuse disorder). It will also ascertain whether or not participants experienced a depressive relapse at four follow-up assessment time points. Also, participant scores ≥ 15 on the monthly PHQ-9 or ≥ 12 on the EPDS gathered remotely will prompt telephone administered relapse determination calls using the MINI. To establish initial reliability, study staff will receive training on MINI administration and will be overseen by [name] at MGH. Evaluators will be blind to treatment condition and will meet biweekly to discuss ratings.

Depressive Symptom Burden

Montgomery-Åsberg Depression Rating Scale (MADRS): The MADRS is a widely used 10-item clinician-rated scale that describes the severity of depressive symptoms.

Edinburgh Postnatal Depression Scale (EPDS): This measure is a 10-item self-report used to measure depressive symptoms.

Patient Health Questionnaire (PHQ-9): The PHQ-9 assesses baseline depression symptom severity and depressive symptom burden.

Patient Health Questionnaire (PHQ-8): The PHQ-8 assesses baseline depression symptom severity and depressive symptom burden. It is the same as the PHQ-9 but does not include the 9th question which asks about suicidal ideation in the past seven days.

Columbia Suicide-Severity Rating Scale (CS-S): The CS-S is used to assess current suicidal ideation and behaviors at baseline and all follow-ups if endorsed on PHQ-9 #9 or EPDS #10 in the UPWARD study. The CS-S will be given at each measurement timepoint in UPWARD-S.

Clinical Global Impression Scale (CGI): The CGI comprises a study staff judgment of illness severity rated on a 7-point global severity scale.

Patient Clinical Global Impression Scale (PGI): The PGI comprises a single-item self-report of severity of illness over the past week on a 7-point likert scale.

Anxiety Symptom Burden

General Anxiety Disorder Questionnaire (GAD-7): The GAD-7 is a 7-item self-report questionnaire that assesses anxiety symptoms.

Pregnancy Specific Anxiety (PSA): The PSA is a 10-item scale to obtain information about pregnancy-specific anxiety and worries.

Perceived Stress

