If a participant scores greater than or equal to 15 on the PHQ-9 or greater than or equal to 12 on the EPDS, the online data collection and management system (REDCap) will automatically provide participants with contact information for national mental health crisis resources and for the research study team. Study investigators will be notified immediately via an algorithm programmed into REDCap. In the UPWARD parent trial and UPWARD-S Arms 1a and 2, study staff at MGH will initiate a clinical response by phone call to assess clinical status and suicidality as soon as possible within 24 business hours of report. The score of 15 is suggested as the threshold for moderate depression.³⁹ Additionally, we will monitor specifically responses to the suicide item (#9) on the PHQ-9: 'Thoughts that you would be better off dead or hurting yourself in some way.' and the suicide item (#10) on the EPDS: 'The thought of harming myself has occurred to me' for all study participants. If a participant endorses either of these items with a score of 1 or greater, REDCap will automatically route participants to fill out the Columbia Suicide Severity Rating Scale (CS-S) and provide participants with contact information for national mental health crisis resources and for the research study team. Study investigators and staff will be automatically notified by the REDCap system for a positive score on questions 3-5 of the CS-S in order to provide outreach as soon as possible within 24 hours and assessment of the patient by a study doctor. In UPWARD-S, endorsement of current suicidal ideation on the SITBI or CCM item (#11) will also automatically route participants to fill out the CS-S. Any endorsement of items 1-5 of the CS-S will prompt administration of the full CS-S to capture duration and intensity of suicidal ideation and/or behaviors. Furthermore, any participant who misses a scheduled assessment point will be contacted immediately by study staff. Study staff will continue to try to reach participants until a participant indicates that they no longer wish to be contacted or the participant has reached six months postpartum by their estimated date of delivery, whichever comes first. Throughout the study, all participants also will be encouraged to contact the study staff at the first sign of increased depression.

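### At the optional 12-15 month UPWARD-Baby survey the automatic response to a high depression score has nothing to act on, because no trigger is set for the PHQ-8

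*Combined protocol and SAP*

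**What the plan says.** Section VII sets a severity rule for the self-report scales: "If a participant scores greater than or equal to 15 on the PHQ-9 or greater than or equal to 12 on the EPDS", REDCap "will automatically provide participants with contact information for national mental health crisis resources and for the research study team". The next step is "Study investigators will be notified immediately via an algorithm programmed into REDCap". A staff call is then added for named components only: "In the UPWARD parent trial and UPWARD-S Arms 1a and 2, study staff at MGH will initiate a clinical response by phone call". A second, separate rule covers the suicide items (PHQ-9 item 9 and EPDS item 10) and routes to the Columbia scale.

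UPWARD-Baby is a one-time REDCap self-report battery offered to parent-trial participants at 12 to 15 months postpartum (Sections IV and V, UPWARD-Baby). The last paragraph of Section VII gives its risk reasoning: "Because we are asking the PHQ-8 at this timepoint instead of the PHQ-9", and so "we will not learn about suicidal ideation and therefore a safety plan for SI is not needed". Section V (Depressive Symptom Burden) describes the PHQ-8: "It is the same as the PHQ-9 but does not include the 9th question".

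**The concern.** The severity rule and the suicide-item rule are two mechanisms. Dropping item 9 explains why the second does not run at 12 to 15 months. It does not explain why the first should stop, since the eight items that measure severity are still asked.

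The women were selected for recurrent depression. If one of them returns a total that the protocol treats elsewhere as needing an automatic response, the plan as written does nothing with it. Section VIII counts possible early identification of worsening symptoms among the benefits for all participants; at this timepoint no written mechanism delivers it. What is at stake is participant safety at one optional assessment.

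**Working it through.** No figure in the plan is at issue. The check sets the provisions side by side and adds one line of arithmetic.

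**1. Inputs to the rule.** There are two: PHQ-9 (cut-off 15) and EPDS (cut-off 12). Section V (Prospective Follow-up and Community Outreach) uses the same scales and cut-offs for relapse determination calls. Feedback to participants under Usual Care rests on the PHQ-9, the EPDS and clinical interviews.

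**2. Which inputs exist at 12 months.** Table 1 has 18 timepoints.

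| Scale | Last mark in Table 1 | At 12 months? |
|---|---|---|
| EPDS | 6 months postpartum | no |
| PHQ-9 | 6 months postpartum | no |
| PHQ-8 | 12 months only | yes |

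Inputs to the rule present at 12 months: 0 of 2.

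**3. Is there a PHQ-8 trigger?** The PHQ-8 appears in three places: Table 1, its description in Section V, and the last paragraph of Section VII. None gives a cut-off, a display or a staff action.

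**4. Would an interview pick it up?** Section V lists five telephone contacts for the parent trial, the last at 6 months postpartum, and describes UPWARD-Baby as self-report. As extracted, the MINI mood, MADRS and CGI rows of Table 1 carry marks at M6, M10 and 12 months. Moved one column to the left, these become third trimester, 3 months and 6 months postpartum. That agrees with the text, and Table 2 places the same rows at third trimester and 3 months postpartum. I read the 12-month marks as a column shift. Even taken literally, those scales do not feed the rule.

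**5. Does the existing cut-off carry over?** PHQ-9 total = PHQ-8 total + item 9, and item 9 cannot be below 0.

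- If PHQ-8 ≥ 15, then PHQ-9 ≥ 15 + 0 = 15, so the parent cut-off is always met.
- The converse fails. A PHQ-8 of 14 with item 9 scored 1 gives 14 + 1 = 15 on the PHQ-9, and a PHQ-8 rule at 15 would miss it.

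A PHQ-8 trigger at 15 therefore flags nobody whom the parent PHQ-9 rule would not flag. It needs no new threshold, but it restores only the PHQ half of the rule and slightly less than all of that half.

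**The case against.** The strongest reply is that parent monitoring was never meant to reach this far. The invitation goes to women who have completed UPWARD, the timepoint is described as additional and optional, and Section VII ends outreach for missed assessments at six months postpartum. This part stands to a degree: the text shows where active tracking stops, and a reader should not infer that the protocol promised active follow-up to 15 months and then broke that promise. But the sentence on missed assessments does not limit the score rule. The automatic tier is written for any participant, and only the staff call is restricted by component. Extension women, who have no follow-up interviews, are not excluded from the automatic tier.

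A second reply is that help is available anyway. Section VII says "all participants also will be encouraged to contact the study staff at the first sign of increased depression", a community provider was required at entry (Section III), Section VIII promises information on national services, and staff review safety concerns with the investigators twice weekly (Section IX). Staff also contact women who do not start the survey, though about taking part. The UPWARD-Baby consent form, removed from the text available here, may list resources. All this lowers the consequence. None of it responds to a score, and a form read before the survey cannot do so.

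A third reply concerns cost. A reader might infer that notification and a phone call should be restored as well, at little expense. The documents do not support that. The parent-trial call assesses suicidality, whereas a team alerted here would hold a high total, no item 9 and no suicidal-ideation plan. The relying site's data access is described for reminders and later analysis. This objection stands, and it limits the fix to the display.

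**Conclusion.** The gap is real and small. The severity rule has no input at the 12-15 month survey, no PHQ-8 trigger replaces it, and the stated reasoning does not address severity. It is worth closing because the response, the platform and the cut-off already exist.

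Two stronger readings should be set aside. One is that leaving out a suicidal-ideation plan is itself an error: the protocol makes that choice openly and gives its reason, and this point does not contest it. The other is that a given number of women would be missed. The documents give neither the opt-in rate nor the share scoring 15 or more at 12 to 15 months, and only completers are invited, so no count can be derived.

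The conclusion rests on three assumptions: that the 12-month interview marks in Table 1 are a column shift; that no PHQ-8 trigger has been programmed without being written down; and that any resources in the consent form are general and not linked to a score. If REDCap already does this, a sentence saying so settles the matter.

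**What to change.** In Section VII, make two one-sentence changes.

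- In the paragraph with the severity rule, add that on the 12-month UPWARD-Baby survey a PHQ-8 total of 15 or more triggers the same automatic display of national crisis resources and study-team contacts.
- In the closing paragraph on UPWARD-Baby, add a cross-reference to that rule, so that the statement on suicidal ideation is not read as covering severity too.

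The cost is one extra REDCap display rule and the two sentences. With display alone, the suicidal-ideation sentence can stay.

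Investigator notification and phone follow-up should be left to the sponsor. They would need a named recipient (parent team or relying site), a short response procedure, and a fresh look at whether the suicidal-ideation sentence still holds once someone is alerted to a high score.
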